6.1 Analyses for Regular Safety External IDMC Meetings

The first external IDMC meeting will be held once 8 participants in Cohort A or Cohort B Part 1 have completed at least 12 weeks of treatment or discontinued permanently. Subsequent external IDMC meetings will occur every four months. Additional meetings may be scheduled by the IDMC.

Details of analyses for IDMC meetings are specified in a separate interim IAP provided in appendix 18.3.

6.3 Interim Analyses for Cohort B Part 1

Two interim analyses will be conducted after 60 participants in Cohort B Part 1 have completed at least 12 weeks of treatment or discontinued the study intervention prematurely. Participants enrolled in Cohort B after those ~60 Cohort B Part 1 participants and prior to the data cut-off date (i.e., in Cohort B Part 2) will not be part of the analysis. The data cut-off applies to all the cohorts and studies used in the analyses, namely the ongoing Phase Ib study NCT04647708: participants from Cohort A and the ongoing Phase Ib study NCT04647708 randomized prior to the cut-off date will be included in the interim analyses.

These interim analyses aim at:

- The first interim analysis will evaluate whether to terminate Cohort B for futility or potentially adapt Cohort B Part 2 dose levels and randomization ratio based on the predictive probability of achieving a significant difference of enpatoran 100 mg BID vs placebo at Week 24 at the final analysis, given the interim data on BICLA response at Week 24. The methodology and the pre-specified rules are described in the interim IAP.
- A second interim analysis will be conducted at the same time to support potential adaptation of dose group(s) and randomization ratio for Cohort B Part 2 (e.g., assigning newly enrolled participants to other dose levels, adapting the randomization ratio) to improve dose-finding in SLE. These adaptations will not apply to participants randomized in Cohort B Part 2 prior to the adaptation decision. Information on the input data, methodology and the guiding principle underlying the recommendation for adaptation are provided in the interim IAP.

Details of these interim analyses are specified in a separate interim IAP provided in appendix 18.3.

6.4 Primary Analysis for Cohort A

This analysis will be the primary analysis for Cohort A. Related analyses identified in this IAP will be performed after all participants in Cohort A have completed Week 16 visit or discontinued the study early, and the database is partially locked for the analysis. Apart from adverse events and treatment exposure data, only data from Cohort A collected up to Week 16 (or earlier discontinuation) will be part of the analysis.

The analyses to be provided for the primary analysis of Cohort A are specified in the different sections of the IAP and in the table of objectives and estimands from section 5.

6.5 Final Analysis of Cohorts A and B

Related analyses will be performed after all participants (from Cohorts A and B) have completed the safety follow-up visit at Week 26, have entered the long-term extension study as part of a separate Sponsor protocol, or have early discontinued the study, and the database is locked for the analysis. The final analysis of data for Cohort A and Cohort B may be performed at the same time or sequentially at the discretion of the Sponsor depending on the time of each cohort's completion.

The analyses to be provided for the final analysis are specified in the different sections of the IAP and in the table of objectives and estimands from section 5.

7 Changes to the Planned Analyses in the Clinical Study Protocol

Section 8.1: the definition of the FAS has been updated to exclude participants who were not randomized in the cohort they were eligible to. Additionally, participants randomized in Cohort B with no BILAG A and no BILAG B at Day 1 will be excluded from the FAS.

8 Analysis Sets and Subgroups

8.1 Definition of Analysis Sets

Each analysis set will be described for each cohort separately, unless specified otherwise.

Screening Analysis Set (SCR)

The screening analysis set (SCR) includes all participants who signed the informed consent, regardless of the participant's randomization and study intervention status in the study.

Full Analysis Set (FAS)

The Full Analysis Set (FAS) will include all participants randomized in the cohort to which they were eligible. Participants with SLE included in Cohort A with ≥ 1 BILAG A score and/or ≥ 2 BILAG B scores at Screening and participants with SLE included in Cohort B with no BILAG A score and ≤ 2 BILAG B scores at Screening will be excluded from the FAS. Participants randomized in Cohort B with no BILAG A and no BILAG B at Day 1 (randomization) will also be excluded from the FAS. Participants will be analyzed according to the study intervention assigned at randomization as per the intent-to-treat principle. For participants who were randomized by mistake more than once with different participant identifiers, the first randomization will be used in this analysis set.

Safety Analysis Set (SAF)

The Safety Analysis Set (SAF) will include all participants, who were administered any dose of any study intervention. Participants will be analyzed per the first actual study intervention they received.

PK Analysis Set (PKAS)

The PK Analysis Set (PKAS) is a subset of the SAF and will consist of all participants, who receive at least one dose of study intervention, have no important events affecting PK, and provide at least one measurable post-dose concentration. A measurement below lower limit of quantification (BLQ) is considered a valid measurement. Participants will be analyzed per the actual study intervention they received.

Pharmacodynamic Analysis Set (PDAS)

The PD analysis set (PDAS) will include all participants who received at least one dose of study intervention, have no important events affecting PD, and have at least one baseline higher or equal to the lower limit of quantification (LLOQ) and one measurable PD endpoint post-dose. Participants will be analyzed per the actual study intervention they received. Important events affecting PD include participants with SLE included in Cohort A with ≥ 1 BILAG A score and/or ≥ 2 BILAG B scores at Screening and participants with SLE included in Cohort B with no BILAG A score and ≤ 2 BILAG B scores at Screening.

Analyses per Analysis Set

The following table summarizes the use of the analysis sets in the different analyses.

	Analysis Set			
Analyses	FAS	SAF	PKAS	PDAS
Demographics and Other Baseline Characteristics	✓			
Previous and Concomitant Therapies	✓			
Study Intervention: Compliance and Exposure		√		
Efficacy Analyses	✓			
Safety Analyses		✓		
Pharmacokinetics			✓	
Pharmacodynamics				✓

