5.1 Inclusion Criteria

Participants are eligible to be included in the study only if all the following criteria apply:

Age

1. Are \geq 18 to \leq 75 years of age at the time of signing the informed consent. Sites should follow their local guidelines for the minimum age required to sign the informed consent.

Vaccinations

2. Are up to date, according to local guidelines, with vaccination against Streptococcus pneumoniae and influenza virus (as seasonally required for influenza virus).

Active SCLE and/or DLE (Cohort A)

- 3. Diagnosis of SCLE or DLE documented in medical history. Predominant findings of active lupus rash must be SCLE and/or DLE. a case-by-case basis if their main diagnosis is active SCLE and/or DLE. Diagnosis must include one of the following options:
 - a. Historical skin biopsy (i.e., pathology report; punch or shave biopsy) within 10 years prior to Screening visit and confirmation of current diagnosis by skin photography at Screening visit.

OR

b. Fresh punch skin biopsy at Screening visit.

OR

- c. If target lesion is unsuitable for biopsy (e.g., malar rash, bridge of the nose), skin photography at Screening visit may be allowed on a case-by-case basis.
- 4. Disease duration of \geq 6 months from time of diagnosis to Screening.
- 5. CLASI-A \geq 8 at Screening Visit; this must be confirmed at Day 1 Visit.

Active SLE

6. Diagnosis of SLE and fulfil Systemic Lupus International Collaborating Clinics (SLICC) classification criteria (Petri 2006), and/or ≥ 4 ACR classification criteria (Hochberg 1997) and/or EULAR/ACR 2019 classification criteria (Aringer 2019).

- 7. Disease duration of ≥ 6 months from when participant met 2012 SLICC, and/or 1997 ACR (Hochberg 1997), and/or 2019 EULAR/ACR classification criteria for SLE until Screening Visit.
- 8. Positive test results for ANA (human epithelial cell-2 ANA ≥ 1:80) and/or anti-dsDNA antibody (≥ 15 IU/mL) and/or anti-Smith antibody during Screening Period.
- 9. Presence of either Scenario 1 OR Scenario 2 (See Figure 1).

Scenario 1 (Cohort A – predominantly active lupus rash):

• Cutaneous lupus erythematosus disease area and activity index (CLASI-A) ≥ 8 at Screening Visit and confirmed at Day 1 Visit.

AND

British Isles Lupus Assessment Group (BILAG 2004) 1B, C, D (i.e., No BILAG 2004 A and No BILAG 2004 ≥ 2B) at Screening visit.

OR

Scenario 2 (Cohort B – moderate to high systemic disease activity):

[figure not shown]
• BILAG $2004 \ge 1$ A or 2B at Screening Visit;

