9.3 Analyses Sets

The analysis populations are specified below. The final decision to exclude participants from any analysis population will be made during a blinded data review meeting prior to database lock and unblinding. The following analysis set definitions will be considered for each cohort.

Analysis Set	Description	
SCR	All participants, who provided informed consent, regardless of the participant's randomization and study intervention status in the study.	
FAS	All participants who were randomized to study intervention. Participants will be analyzed per the intervention group to which they were randomized, following the intention-to-treat principle. All participants, who were administered any dose of any study intervention. Participants will be analyzed per the actual study intervention they received.	
SAF		
PK	All participants, who receive at least 1 dose of study intervention, have no important events affecting PK, and provide at least 1 measurable post-dose concentration. Participants will be analyzed per the actual study intervention they received. All PK analyses will be based on this analysis set.	
PD	All participants, who receive at least 1 dose of study intervention, have no important events affecting PD, and have a Baseline, and at least 1 measurable PD endpoint post-dose.	
	Participants will be analyzed per the actual study intervention they received. All PD analyses will be based on this analysis population.	

FAS = Full Analysis Set, PD = Pharmacodynamics, PK = Pharmacokinetics, SAF = Safety, SCR = Screening

CCI			
	-		
_			
CCI			

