	Population: Participants with active SCLE, DLE or SLE with active lupus rash. Note: Cohort A participants OR Cohort B participants with CLASI-A ≥ 8. For FACIT-Fatigue: Cohort A participants.		
	Population-Level Summary: Descriptive statistics at each visit and treatment difference at Week 24 as estimated by MMRM		
To evaluate the efficacy of enpatoran compared to placebo in patient-reported symptoms, in participants with active SLE	Endpoints: Change from Baseline in the Functional Assessment of Chronic Illness Therapy (FACIT)-Fatigue scores at Week 24	14.3.14	Final
	Population: Participants with active SLE Note: Cohort B participants		
	Population-Level Summary: descriptive statistics at each visit and treatment difference at each study visit as estimated by MMRM		

Cohort A: participants with active SCLE, DLE or SLE with predominantly active lupus rash, defined as patients with SCLE, DLE or SLE and a CLASI-A score at ≥ 8 at Screening and confirmed at Day 1.

Cohort B: SLE participants with active lupus rash, i.e., who have moderate to high systemic disease activity (BILAG ≥ 1A and/or 2B) with 1 or 2 of the following: CLASI-A ≥ 8 and/or

MCP-Mod: Multiple Comparison Procedure – Modeling.

6 Overview of Planned Analyses

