14.2.4 Supplementary Analyses of the Primary Estimand

Supplementary analyses described in this section will be performed on all participants from Cohort B (parts 1 and 2 combined). Intercurrent events will be handled similarly to the primary estimand.

CONFIDENTIAL INFORMATION Summary statistics for the BICLA response will be summarized during the on-treatment period. The conditional treatment effect on BICLA response at Week 24 will be estimated using a logistic regression model with study intervention group and stratification factors.

Odds ratios and associated two-sided 95% Wald confidence intervals will be provided for each active group versus placebo and will be converted into differences to placebo and their 95% confidence intervals.

An additional supplementary analysis may be performed if 34 Cohort B participants or more (\sim 10 % of the planned sample size in Cohort B) are included in the FAS with no BILAG A score and less than 2 BILAG B scores at Baseline. If this threshold is reached, then the primary analysis described in Section 14.2.1 will be conducted on the subset of the FAS who had at least one BILAG A score and/or \geq 2 BILAG B scores.

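### The Cohort B exclusion in SAP 8.1 uses ≤ 2 BILAG B scores where < 2 fits the entry rule, so eligible participants with exactly two Bs and no A fall out of the FAS and PDAS

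*SAP*

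**What the plan says.** Protocol Section 5.1, inclusion criterion 9, Scenario 2, sets the Cohort B BILAG threshold at one or more A scores, or two Bs: "A or 2B at Screening Visit". A CLASI-A and/or SLEDAI condition applies as well. The note under the objectives table in SAP Section 5 describes Cohort B in the same way, as SLE participants "who have moderate to high systemic disease activity (BILAG ≥ 1A and/or 2B".

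Protocol Section 9.3 defines the FAS as "All participants who were randomized to study intervention". SAP Section 7 announces a departure from this: "the definition of the FAS has been updated to exclude participants who were not randomized in the cohort they were eligible to". It adds one further removal, of Cohort B participants with neither an A nor a B at Day 1.

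SAP Section 8.1 then gives the operative definition. It opens by saying that the FAS "will include all participants randomized in the cohort to which they were eligible". For Cohort A it removes SLE participants with at least one A and/or at least two Bs at Screening. For Cohort B it removes those with "no BILAG A score and ≤ 2 BILAG B scores at Screening will be excluded from the FAS". The PDAS definition repeats the condition, counting among the events that affect PD "participants with SLE included in Cohort B with no BILAG A score and ≤ 2 BILAG B scores at Screening".

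**The concern.** The Cohort B exclusion is meant to catch participants who did not meet the Cohort B entry rule. That rule fails only when there is no A and at most one B. A cut-off of ≤ 2 reaches one score too far and takes in participants who entered correctly with two Bs.

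The FAS is the set for all efficacy analyses, including the Cohort B primary BICLA test (SAP Section 14.2) and the Cohort B efficacy secondaries. The PDAS carries the PD analyses. Applied literally, the rule confines the analysed Cohort B population to participants with an A or at least three Bs at Screening. That is narrower than the population named in the estimand, and it costs sample size. Safety analyses use the SAF and are not touched.

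**Working it through.** **Logic check.** Inputs are the Cohort B BILAG entry rule (Protocol 5.1: A ≥ 1 or B ≥ 2), the Cohort B exclusion as written (SAP 8.1: A = 0 and B ≤ 2), and the same exclusion with the sign changed (A = 0 and B < 2). All counts are at Screening.

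| A | B | Meets Cohort B BILAG entry | Excluded as written (≤ 2) | Excluded with < 2 |
|---|---|---|---|---|
| 0 | 0 | no | yes | yes |
| 0 | 1 | no | yes | yes |
| 0 | 2 | **yes** | **yes** | no |
| 0 | 3 or 4 | yes | no | no |
| 1 | 0 to 4 | yes | no | no |

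This covers ten states (A = 0 or 1, B = 0 to 4). The written rule conflicts with eligibility in exactly one of them, no A and two Bs. With < 2 there is no conflict, and the exclusion is the exact complement of the BILAG entry rule.

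**Other passages on the boundary.** The Cohort A limb of SAP 8.1 removes participants with two or more Bs, so the two-B profile fits neither cohort's FAS. SAP 11.3 grades at least two Bs with no A as moderate, and at most one B with no A as mild. SAP 14.2.4 separates fewer than two Bs from two or more. These last two apply at Baseline, so they show where the authors place the boundary but do not override a Screening rule. The note in SAP 14.2.1 on participants in the FAS with a single B does not state a Screening cut-off either.

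**Scale.** The share f of Cohort B with exactly two Bs and no A at Screening is not in the documents, and the Cohort B power is redacted. Both are assumed below.

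- Base sizes: 60 + 280 = 340 without dose adaptation; 340 + 92 = 432 at the ceiling (Protocol 9.2).
- Number lost = f × 340, or f × 432.
- Standard-error inflation = 1/√(1 − f).
- Approximate power = Φ((1.96 + z) × √(1 − f) − 1.96), where 1.96 + z is 2.80 for 80% starting power and 3.24 for 90%. This assumes the same treatment effect in those retained.

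| Assumed f | Lost of 340 | Lost of 432 | SE factor | Power from 80% | Power from 90% |
|---|---|---|---|---|---|
| 5% | 17 | 22 | 1.026 | 78% | 88% |
| 10% | 34 | 43 | 1.054 | 76% | 87% |
| 20% | 68 | 86 | 1.118 | 71% | 83% |
| 50% | 170 | 216 | 1.414 | 51% | 63% |

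For comparison, SAP 14.2.4 says an extra analysis of the primary result "may be performed if 34 Cohort B participants or more" are in the FAS with fewer than two Bs and no A at Baseline. It describes that count as roughly 10% of the planned Cohort B size, and 0.10 × 340 = 34 reproduces it. That is a different group of participants; it serves only to show what the SAP regards as a material number.

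**The case against.** The strongest objection is that the point turns on one comparison sign, and signs in the public SAP text are not always reliable. The treatment-duration categories in Section 13 overlap at each cut-point, and one split of corticosteroid dose in Section 12 omits the value 10. An error in the PDF text is therefore possible. Against that, ≤ 2 appears identically in two separate definitions while the ≥ signs in the same sentences read correctly. A check against the source settles it, and the fix begins there.

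A second objection is that the intended rule can be recovered from the opening sentence of the FAS definition and from SAP Section 7. In addition, the blinded data review (Protocol 9.3) and the listing of exclusions (SAP 10.2.2) would probably expose the problem. That is fair as to intent and detection. But neither step amends the definition: restoring these participants at the review would depart from the written SAP, and following the SAP would drop them.

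Two limits on the size also stand. The power figures come from a single normal test, whereas the primary test combines a Part 1 logistic test and a Part 2 MCP-Mod test with fixed weights, so they are approximate. And because the criterion is measured before randomization, the harm is lost precision and a changed population; neither bias between arms nor type I error inflation has been shown.

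**Conclusion.** The concern holds. As written, SAP 8.1 excludes from the Cohort B FAS and PDAS participants who satisfy the Cohort B BILAG entry rule with two Bs and no A. This contradicts the protocol, SAP Section 5, SAP Section 7 and the first sentence of the FAS definition itself. It is most likely a slip for < 2, but it sits in the operative definition of the primary efficacy set and must be corrected.

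The contradiction does not depend on how many participants are affected; the practical damage does. At an assumed 10% share, 34 of 340 participants would be lost and an assumed 80% power would fall to about 76%. At an assumed 50% share, the figures are 170 and about 51%.

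**What to change.** Before database lock and unblinding for the Cohort B analysis:

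1. Check the sign in the source SAP.
2. If it reads ≤ 2, change the Cohort B condition to no BILAG A and < 2 BILAG B scores at Screening, in both the FAS and the PDAS definitions. This brings the exclusion into line with Protocol 5.1 and SAP Section 7.
3. Report how many randomized Cohort B participants the old wording would have excluded.

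The cost is one character in two places plus one count. Trial conduct does not change.

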8.2 Subgroup Definition and Parameterization

Subgroup analyses will be performed for primary efficacy variables (BICLA response at Week 24 in Cohort B [section 14.2.5], CLASI-A total score at Week 16 in Cohort A [section 14.1.6]), selected key secondary variables (SRI-4 response at Week 24 in Cohort B [14.3.6]), and CCI

The category "missing" will not be included in any subgroup analysis. In Cohort A, subgroup analysis will be performed if at least 5 participants are observed in all subgroup levels for each study intervention group. The threshold will be set to 10 for subgroup analyses in Cohort B.

• Systemic CS use at Baseline: low/medium (daily prednisone-equivalent dose < 10 mg), high (daily prednisone-equivalent dose ≥ 10 mg)

The following subgroups will be defined for Cohort A only:

• Disease diagnosis (CLE only, SLE)

CLE only: "Does the subject have a diagnosis of SLE" = No and participant has DLE and/or SCLE

SLE: "Does the subject have a diagnosis of SLE" = Yes

• CLASI-A total score at Baseline: $< 10, \ge 10$

The following subgroups will be defined for Cohort B only:

• Ethnicity: Japanese, non-Japanese

The following subgroups will be defined for Cohort B with CLASI $A \ge 8$ at Screening and confirmed at Day 1:

• CLASI-A total score at Baseline: $< 10, \ge 10$

9 General Specifications for Data Analyses

Unless otherwise specified, data will be summarized for each cohort (Cohort A, Cohort B) separately.

Study intervention groups will be labeled placebo, enpatoran 25 mg BID and enpatoran 50 mg BID, enpatoran 100 mg BID, as applicable for the cohort/part. Study intervention groups may also be referred as "dose levels".

Unless otherwise specified, comparisons will be presented for each active dose of study intervention versus placebo. Results from different study intervention groups will be presented in increasing order of dose level (placebo on the left).

Unless otherwise specified, continuous variables will be summarized using descriptive statistics, i.e., the number of participants with non-missing values (n), mean, standard deviation, median, 25th percentile (Q1) and 75th percentile (Q3), minimum, and maximum.

Qualitative variables will be summarized by frequency counts and percentages. Unless otherwise stated the calculation of proportions will be based on the number of participants of the analysis set of interest. Therefore, counts of missing observations will be included in the denominator and presented as a separate category.

Unless otherwise specified, descriptive statistics by nominal visit or time point, e.g., for laboratory measurements, will include data from both scheduled and unscheduled visits after applying visit/time windowing (section 9.7). Unscheduled visits will also be included in the derivation of baseline or worst post-baseline values.

CC

If confidence intervals are

to be calculated, these will be two-sided with a confidence probability of 95%, unless otherwise specified in this IAP.

In order to provide overall estimates of study intervention effects, data will be pooled across sites. The "site" factor will not be considered in statistical models due to the high number of participating sites in contrast to the anticipated small number of participants randomized at each site.

All statistical analyses described in this IAP will be performed using SAS® software version 9.4 or higher apart from the analysis of the primary estimands using the MCP-Mod approach which will be performed using R version 4.1.3 or higher. Phoenix® WinNonlin® version 8.3 or higher (Certara, L.P., Princeton, New Jersey, USA) will also be used to derive PK parameters.

